Study Protocol

IRB ID: 20180597 (CR00012479)

Study Number: 1 R34 DA043784-01A1

Date: July 19, 2018

Study Title

Culturally Modified Family Based Therapy for Haitian Youth in South Florida
(CIFFTA).

NCT number: 03876171

Date: July 19, 2018

INSTRUCTIONS:

1) Protocol Title

Culturally Modified Family Based Therapy for Haitian Youth in South Florida (CIFFTA).

2) IRB Review History*

None

3) Objectives*

The study will pursue the following Specific Aims:

Aim 1. To adapt CIFFTA and the assessment instruments necessary to test its efficacy to the unique Haitian sociocultural contexts. This process of adaptation has the purpose of optimizing CIFFTA's acceptability and cultural appropriateness. It will rely on ethnographic methods (participant observations, focus groups, and interviews) to guide the adaptation process.

Aim 2. Determine, via a pilot efficacy trial, the impact of CIFFTA compared with standard-of-care for reduction of drug use, risky sexual behaviors, and delinquency risk among Haitian adolescents ages 13 to 17 in Miami-Dade County. The ethnographic component of the study will monitor the delivery of the intervention, collecting process data, and affording the investigators needed perspective on the intervention's impact.

Aim 3. To generate preliminary data on the usefulness of assessment tools and CIFFTA's efficacy among the population. These data will help evaluate the effect of the intervention and its best form of implementation. They will also provide preliminary evidence to justify a full clinical trial of CIFFTA in a population of at-risk Haitian youth.

Primary study outcomes include: intervention attendance and completion; sustained abstinence in substance use through biochemical verification and self-report; family functioning; sexual risk behavior; and conduct disorder. Secondary outcomes include: recidivism in delinquency, improvement in family communication, and peer/gang involvement. Outcomes will be assessed through follow-up instruments at three points: 3, 6 and 12 months.

4) Background*

Despite preventive efforts made over the last three decades, it is clear that some populations have not benefited from attempts to deter them from risky behaviors. Haitian youth constitute an important but understudied population who may be particularly

Study Protocol

IRB ID: 20180597 (CR00012479)

Study Number: 1 R34 DA043784-01A1

Date: July 19, 2018

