Ethnographic methods will be employed including: in-depth interviews; focus group discussions; and observation of participating families in daily life. The ethnographers will conduct observations as the study begins and during follow-up data collection. With regard to Aims 1 & 3, the ethnographic observations and interviews help the research team to monitor the fidelity of the intervention. Ethnographic data will also help to define the processes by which change takes place. To summarize: the ethnographic data will: a) guide the development and implementation of the intervention (see also timeline); b) enable us better to understand barriers and facilitators to change that will inform further modification of family-based interventions of this kind; and c) facilitate interpretation of the outcome analysis results.

In order to give the study a chance of determining the intervention's impact in preventing drug use, we intend to collect urine samples at baseline and all follow-up time points. The urine tests will not be the only measures of drug use employed during the follow-up period, but in an institutional setting like the JAC, they are likely to be the most accurate.

Field observations. Ethnographers will be trained to capture processes and describe events, communications, behaviors, activities and cultural materials that make up the particular contexts in which Haitian live. They

Study Protocol

IRB ID: 20180597 (CR00012479)

Study Number: 1 R34 DA043784-01A1

Date: July 19, 2018

will make regular visits to pre-selected, highly frequented locales, gendered or not, where Haitian youths "hang out."

In-depth Interviews. In-depth interviews will begin after field observations have been initiated, and therefore should benefit from findings of observations in progress. The Interview Guide serves as a preliminary template to be used by interviewers. It will generate information on topics such as (a) life experiences, (b) drug use, (c) identity, (d) lifestyle, (e) personal experiences, such as forms of sociability and beliefs associated with youth behaviors and the juvenile justice.

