Youth Urine Toxicology. As part of our research component, we plan to collect voluntary urine specimens for analysis at the times of the youths' initial and follow- up interviews in order to validate self-report. We will follow procedures informed by NIDA's CJDATS workgroup guidelines. Urine specimens will not be collected on youths incarcerated for more than two days. The use of four substances will be probed using the Onsite CupKit® urine screen procedure (positive threshold levels are noted in parentheses): (1) methamphetamines (500 nanograms per milliliter [ng/ml] of urine), (2) opiates (300 ng/ml of urine), (3) cocaine (300ng/ml of urine), and (4) marijuana (THC) (50 ng/ml of urine). The surveillance window for the four drugs is as follows: methamphetamines and opiates = 48 hours; cocaine = 72 hours; marijuana: moderate users = 5 days; heavy users = 10 days; chronic users = 20 days. Although we considered hair analysis, urine screens were selected because of they are the most widely used and accepted method for supervision monitoring (Lipsey & Wilson, 1998), they are minimally invasive, can be collected in the community during follow-up assessments and carry fewer taboos on collection (Meyers et al., 2002). Urine screen results will be kept confidential, and will be collected in containers marked with pre-printed labels without personal identifying information. To assure integrity of the sample, the Onsite CupKit® automatically checks for temperature, and the interviewer will ensure that there is no one else in the restroom.

Overview of Assessment Procedures and Attrition

The 3-month follow-up assessment will be measured from the end of the intervention, as will be the 6-month and the 12-month follow-up

Study Protocol

IRB ID: 20180597 (CR00012479)

Study Number: 1 R34 DA043784-01A1

Date: July 19, 2018

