To ensure the consistency and integrity of the independent variables, project research assistants will record on a regular basis all random assignments, other contacts, and assessments. These records will be audited regularly by the PI and Co-Is. To ensure high quality data, all research staff will be closely trained in proper data collection and entry. All data will be checked promptly after collection for completeness, quality, and accuracy. This will include screenings for out-of-range values and missing data. Apparent anomalies will be immediately brought to the attention of the interviewer for clarification and any indicated follow-up. We will monitor three key outcome measures on a bimonthly basis.

For urine tests:

Urine specimens will be collected using the Onsite CupKit®, which produces test results within 3 to 5 minutes. As such, no biological specimens will be kept for storage.

Urine specimens will be collected, but not stored.

Because youths tend to underreport the use of such socially disapproved drugs as cocaine (Dembo & Schmeidler, 2002), urine testing is a valuable component of our data collection plan. Based on previous experience conducting research on delinquent youth (e.g., Dembo & Schmeidler, 2002), and because the urine test data will be treated as confidential, we anticipate a low rate of refusal to provide a

Study Protocol

IRB ID: 20180597 (CR00012479)

Study Number: 1 R34 DA043784-01A1

Date: July 19, 2018

specimen at each time point. If preliminary analyses at each data collection point indicates a low concordance rate ($\kappa < .80$) between self-reported use and urine toxicology results for a given drug (e.g., marijuana) both self-report and urine test results will be used to construct drug use measures for our analyses (e.g., self-reported use or a positive urine test = use; no self-reported use and a negative urine test = no use). If a high concordance rate is found ($\kappa > .80$), the self-reported use data for that drug will be used.

13) Provisions to Monitor the Data to Ensure the Safety of Subjects*

All data collection protocols include Informed Consent Forms. They also include Confidentiality Safeguards, Mandatory Reporting Safeguards, Staff Training Safeguards, Data Safeguards, Discomfort with Assessment Procedures or Disclosure Safeguards, and Dissatisfaction Safeguards. In addition, the PI will constitute an external Data safety and Monitoring Board (DSMB).

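### When κ exceeds .80 a drug is scored on self-report alone, so a urine-positive youth who denies use counts as not using; this is not reconciled with the biochemically verified abstinence outcome

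*Protocol*

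**What the plan says.** Protocol sections 3 (Objectives) and 9 (Study Endpoints) list among the primary outcomes "sustained abstinence in substance use through biochemical verification and self-report".

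Section 12 (Data Management, urine tests) gives the scoring rule. It opens with "If preliminary analyses at each data collection point" and sets a threshold of κ = .80 for each drug.

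- **κ below .80:** "both self-report and urine test results will be used to construct drug use measures for our analyses". The protocol's illustration is that either source positive counts as use, and both negative counts as no use.
- **κ above .80:** "the self-reported use data for that drug will be used".

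Section 10 (Youth Urine Toxicology) and section 11 give the purpose of the voluntary specimens as "in order to validate self-report". Four drugs are on the panel. Their detection windows run from 48 hours to 20 days, while the self-report windows under Instrumentation run from 30 days to 12 months.

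The SAP's analysis text mentions neither urine, κ nor abstinence. Its example of a drug-use outcome, under Analytic Methods, is an ordinal frequency.

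**The concern.** In the high-κ branch the urine result has no part in the score. A youth whose specimen is positive but who denies use is recorded as not using that drug, although the outcome is described as biochemically verified. Nothing elsewhere in the protocol or SAP overrides this.

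Two features of the wording add to the difficulty. First, κ is examined at each data collection point, but the decision clause names only the drug. The rule can mean one definition per drug for the whole study, or a definition that may differ from visit to visit. Under the second reading, a change of scoring would be mixed with change over time in an outcome that is meant to be sustained. Second, κ of exactly .80 falls in neither branch.

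At stake is the meaning of one of the five primary outcome domains in a pilot intended to inform a full trial.

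**Working it through.** The plan gives no figure on this point to reproduce. The check asks how many denials can pass a κ > .80 test, and how often that would happen.

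**Inputs from the documents.** 80 youths analysed (SAP, Power Analysis); threshold κ = .80 (Protocol section 12).

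**Assumed inputs.** The number of urine positives P, the number of positives who deny use x, and the number of urine-negative youths who report use f. The documents give none of these.

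**Formula.** Of 80 youths, P − x are positive on both sources, x on urine only, f on self-report only, and 80 − P − f on neither.

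- Observed agreement: po = (80 − x − f)/80
- Chance agreement: pe = [(P − x + f)·P + (80 − P + x − f)·(80 − P)]/80²
- κ = (po − pe)/(1 − pe)

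**Step 1: no urine-negative reporters (f = 0).**

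| Urine positives | Deniers | po | pe | κ | κ with one more denier |
|---|---|---|---|---|---|
| 8 | 2 | .975 | .84 | .844 | .750 |
| 16 | 4 | .950 | .71 | .828 | .779 |
| 24 | 6 | .925 | .61 | .808 | .773 |

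For the last row, pe = (18·24 + 62·56)/6,400 = 3,904/6,400 = .61 and κ = .315/.39 = .808. In each row a quarter of the urine positives are scored as not using while the check is passed.

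The switch also creates a jump. With 24 positives and 6 denials, self-report alone counts 18 users (18/80 = 22.5%). A seventh denial takes κ to .773, the combined rule applies, and 24 users are counted (30%).

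κ of exactly .80 can occur: with 40 positives and 8 deniers, po = .90, pe = .50 and κ = .40/.50 = .80.

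**Step 2: urine-negative youths who report use.** Because urine windows are shorter than self-report windows, some youths can truthfully report use and test negative. With 24 positives, the largest number of deniers compatible with κ > .80 falls as follows:

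| Urine-negative reporters (of 56) | 0 | 2 | 4 | 6 | 7 | 8 |
|---|---|---|---|---|---|---|
| Maximum deniers | 6 | 4 | 2 | 1 | 0 | κ > .80 not reachable |

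**Step 3: average loss.** Each of 80 youths is assumed urine-positive with probability 30%, each positive denies with the stated probability, and each urine-negative youth reports use with the stated mismatch probability. The entry is the mean number of positives discarded for one drug at one visit: x if κ > .80, otherwise 0.

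| Mismatch | Range over denial rates of 5–25% |
|---|---|
| 0% | 1.2–3.1 |
| 2% | 1.2–2.4 |
| 5% | 0.7–1.5 |
| 10% | 0.1–0.6 |
| 15% | at most 0.14 |
| 20–30% | about 0 |

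The top value is 3.1/80, or about 3.8 percentage points of measured use.

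**The case against.** The best defence is that the κ check is itself the biochemical verification. The protocol twice gives the purpose of urine as "in order to validate self-report", and a concordance threshold is a recognised way to do that. Where denial is common, κ falls and the combined rule takes over. This explains the rule, and it is why the two statements are better called unreconciled than flatly contradictory. But it validates self-report for the group. It does not establish that a particular youth was abstinent, and step 1 shows that denials survive the check.

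The defence is right on size. The built-in difference in windows makes the high-κ branch less likely, and where mismatch is large the protocol will usually apply the combined rule anyway.

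A reader might infer more than the documents support:

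- **That the rule contradicts the protocol's own statement on under-reporting.** That sentence begins "Because youths tend to underreport the use of such socially disapproved drugs as cocaine" and is confined to drugs of that kind. The per-drug κ check is an imperfect response to it, not a contradiction.
- **That it contradicts the reason for collecting urine.** Section 10 (Ethnography) does link urine to the intervention's "impact in preventing drug use, we intend to collect urine samples at baseline and all follow-up time points", but adds that urine is not the only measure. Collecting specimens at every visit is compatible with a rule on when to use them.
- **That it biases the arm comparison.** The rule makes no reference to arm. A large spurious difference arises only if all deniers are placed in one arm, which nothing in the documents suggests.
- **That the definition will change between visits.** This is one possible reading, not a stated plan.

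**Conclusion.** The concern holds in limited form. The scoring rule in section 12 allows a urine-positive youth to count as not using a drug, and this is not reconciled with a primary outcome that calls for biochemical verification. That conclusion rests on the text alone, as do the visit-by-visit ambiguity and the gap at κ = .80.

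The size rests wholly on assumptions: 30% urine-positive, 5–25% denial and 0–30% mismatch. On these the average is 0 to about 3 of 80 youths per drug per visit, near 0 once mismatch reaches 15%. It applies only to the four tested drugs and only in the high-κ branch. It is not an estimate for sustained abstinence over several visits, nor for the SAP's effect size, because the documents do not say which score enters which model. The SAP also describes its analyses as preliminary. This is a modest, avoidable misclassification that should be corrected; it does not undermine the trial.

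**What to change.** Delete the κ switch. For the four tested drugs, make the combined rule that section 12 now offers as an illustration the fixed definition at every visit and in both arms: use if either self-report or urine is positive, no use only if both are negative. Report κ by drug and visit as description. Give a score from self-report alone as a sensitivity analysis. State in the SAP that the combined score defines the abstinence outcome.

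The cost is a short change of wording in the protocol and SAP. No new data are needed, because specimens are already planned at baseline and every follow-up. Measured use may be slightly higher. Specimens are voluntary, so a visit without one rests on self-report and should be reported as unverified; the protocol expects few of these ("we anticipate a low rate of refusal"). More elaborate handling, such as multiple imputation of missing urine results or a new recall window, is open to debate and is not needed to repair this defect.

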Eighty-eight (88) adolescents aged 13 to17 and their families will be recruited into the study to obtain 80 after attrition. Age, place of residence (Miami-Dade), and Haitian ancestry will constitute the main criteria for selection. Other criteria of inclusion are: adolescents that are NOT incarcerated and with no prior mental health care or history of psychoactive medication, to increase the homogeneity of the sample in terms of a naive population; adolescents in families who have lived in the US for 3 years, to avoid confounding initial culture shock with other conventional aspects of maladjustment; families with a range of organizational structures (nuclear and non-nuclear), to achieve variability and observe differences in family dynamics with regard to response to the intervention. Youths with a documented history of mental retardation and/or organic dysfunction will be excluded; the youths in question will be referred to appropriate agencies.

6) Number of Subjects*

Eighty-eight (88) participants will be recruited into the study. Instruments for the intervention will be pretested with 10 Haitian youth.

7) Study-Wide Recruitment Methods*

This project’s recruitment approach will consist of the following steps: (a) after initial referral by the JSD, potential participants will be approached by the ethnographer who will describe the scope of the study and ask the participant if

Study Protocol

IRB ID: 20180597 (CR00012479)

Study Number: 1 R34 DA043784-01A1

Date: July 19, 2018

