This is a multi-wave study, with approximately all the participants recruited by the end of Year 02 and the remainder in the beginning of Year 03. At baseline, we will conduct comprehensive assessments of all study constructs and repeat all other assessments annually. Activities during the first three months will consist of the following: Staffing, Instrument Calibration, Ethnographic Update. Each wave will be composed of 22 participants to be randomized into two groups (11 each). Each undergo assessment at intake (T1) and outtake (T2), a booster session 3 months after outtake and a final assessment at 12 months. Data analysis process will be initiated at the third month and continue throughout the study implementation.

Study Protocol

[figure not shown]
IRB ID: 20180597 (CR00012479)

Study Number: 1 R34 DA043784-01A1

Date: July 19, 2018

Publications are expected to start from month 20. The table below details the activity processes.

Project Timeline

9) Study Endpoints*

Primary outcomes are: intervention attendance and completion; sustained abstinence in substance use through biochemical verification and self-report; family functioning; sexual risk behavior; and conduct disorder.

Secondary outcomes include recidivism in delinquency, improvement in family communication, and peer/gang involvement.

10) Procedures Involved*

RCT procedures

CIFFTA has three major components – Family-Based Therapy, Individual Therapy, and Psycho-educational Modules – delivered over 16 weeks in a six sessions (60 minutes each) per month format. In this study, the therapy will be delivered in the home to reduce missed sessions and premature termination. Special training will focus on how to structure the home environment to reduce distractions. Three sessions per month will typically be a session which may include Family-based Therapy or Psycho-educational modules with the family or parents alone (e.g., parent training). The other three sessions are typically with the adolescent alone and include Motivational Interviewing or Psycho-educational modules designed for the adolescent.

Study Protocol

IRB ID: 20180597 (CR00012479)

Study Number: 1 R34 DA043784-01A1

Date: July 19, 2018

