CIFFTA uses a flexible manual that allows for tailoring of the intervention through the selection of psycho-educational modules that address specific family and adolescent clinical and cultural issues that are central to that lives of that family. Individual and family level targets of change must be specifically able to address the ecological factors as well. For example, parenting practices may be improved to better monitor the adolescent's peers; parental leadership and guidance may focus on taking a more active role in advocacy in schools and in teaching adolescents how to handle racism and discrimination; and adolescent skills may become important in better addressing peer pressure in the peer context.

Overall intervention process.

Study Protocol

IRB ID: 20180597 (CR00012479)

Study Number: 1 R34 DA043784-01A1

Date: July 19, 2018

Pretest. CIFFTA instruments only will be pretested with a subsample of 5 Haitian youths and their families. Youths and families will be selected purposefully and will NOT be included in the study sample. Because the whole trial is consist of testing the applicability of CIFFTA within this population, the study will not be tested prior implementation. The instruments will be tested for fidelity of translation.

Study Process. Randomization will be done after baseline data are logged and will be carried out via computer-generated sequential assignment; in that sense, interventionists do not control randomization and interviewees will be blind to condition. At baseline, we will conduct comprehensive assessments of all study constructs and repeat all other assessments (see timeline). Outcomes anticipated will include lowered risk for re-offending (i.e. YLS scores), rates of recidivism (i.e. re-arrest), drug/alcohol use, and improved psychological adjustment and family functioning of those youths in the intervention group relative to those in the comparison group. Similarly, we expect parents/caregivers of these youths to see improvement in their child's behavior (i.e. less conduct disorder reported) and improved family functioning overall.

Ethnography.

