Participants' contact information will be entered into the confidential password-protected tracking system. Their study information, however, will be de-identified in a separate file. If at the time of assent, consent or if it has been determined later

Study Protocol

IRB ID: 20180597 (CR00012479)

Study Number: 1 R34 DA043784-01A1

Date: July 19, 2018

that a participant is no longer eligible, the participant will be discontinued from the study and told that the study inclusion criteria are no longer met. All information regarding that participant will be destroyed. Every precaution will be taken to prevent any violations of confidentiality. Confidentiality of subject records is assured by assigning the participants research numbers and storing computer files without identifying information. A single password-protected file with identifying information will be kept for tracking purposes only. Only [name], [name] and the Postdoc will have access to the password protected files. All personal information and data contained in computer systems will be password-protected and stored in locked facilities. Paper records are kept in locked file drawers in a locked room.

This study will have an extended NIDA Certificate of Confidentiality to protect the subjects' confidentiality.

27) Provisions to Protect the Privacy Interests of Subjects

Parents/guardians and youths who are interested in participating in the project will be informed that project services are provided in-home, confidential, and that participation is voluntary. Interviews will be done at a comfortable place chosen by the study participant where there is no intrusion from a third party and where participant feel safe providing response to questions, examinations, and procedures.

Trained research staff will ensure participants of the study that all information regarding that participant will be destroyed and that every precaution will be taken to prevent any violations of confidentiality. Confidentiality of subject records is assured by assigning the participants research numbers and storing computer files without identifying information.

28) Compensation for Research-Related Injury

Not applicable.

29) Economic Burden to Subjects

There is no cost to participate in this study.

Consent Process

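### The rule to destroy all data on a youth later found ineligible has no cut-off at randomisation, and if applied to a randomised youth it conflicts with intent to treat

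*Protocol*

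**What the plan says.** Protocol section 26 (Confidentiality) opens the rule with "If at the time of assent, consent or if it has been determined later". A participant judged no longer eligible is then taken out of the study, not only out of treatment, and is "told that the study inclusion criteria are no longer met. All information regarding that participant will be destroyed". The rule does not mention randomisation and makes no exception for coded outcome data. Section 27 has a related sentence: "Trained research staff will ensure participants of the study that all information regarding that participant will be destroyed".

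Other parts of the protocol bear on this:

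- **Order of events.** Section 24 places signed assent and consent before any other study activity, followed by the baseline interview. Section 10 (Study Process) adds: "Randomization will be done after baseline data are logged".
- **Follow-up and analysis.** Section 10 (Overview of Assessment Procedures and Attrition) commits to following everyone who enters, including those who leave treatment early, and to intent to treat in both assessment and analysis.
- **Eligibility.** Section 5 requires youths "with no prior mental health care or history of psychoactive medication".
- **Sample size.** Section 5 states: "Eighty-eight (88) adolescents aged 13 to17 and their families will be recruited into the study to obtain 80 after attrition".
- **Records.** Section 12 has research assistants record all random assignments and assessments. Section 13 destroys the participant identifier at the end of the study, which is narrower than destroying all information.

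Section 14 (Withdrawal) deals with adverse events, not with ineligibility. The SAP text available for review does not take up the matter.

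**The concern.** Consent comes first, then baseline, then randomisation. A rule that runs from consent to an unspecified later time can therefore reach past randomisation. A randomised youth cannot be both erased and followed, so the two sections cannot both be carried out for that youth.

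Excluding a randomised youth from the main analysis is usually a reversible choice: the data remain, and a second analysis can put the youth back. Destruction removes that option. Neither the likelihood-based or Bayesian handling of missing data that the SAP plans, nor any sensitivity analysis, can use outcomes that no longer exist. The assignment log might still show how many youths were lost from each arm, unless it too counts as information to be destroyed.

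If the erased youths resemble those kept, only precision suffers. Bias in an arm comparison needs more: for example, that erasure is related to outcome and differs between arms in number or type.

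**Working it through.** **1. The passages side by side**

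| When ineligibility is found | Section 26 | Section 10 | Conflict? |
|---|---|---|---|
| At assent or consent | Out of study, data destroyed | Not yet randomised | No |
| After consent, before randomisation | Same | Not yet randomised | No |
| After randomisation, criterion never met | Same, on the wording | Follow and analyse by intent to treat | Yes |

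The first two rows remove no randomised youth. The third row is the whole of the point. It is possible because a criterion based on history can prove false after entry, and no section describes a formal check of mental health or medication history before randomisation.

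**2. The plan's own allowance**

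88 − 80 = 8 youths, and 8/88 = 9.1%. This agrees with the SAP's statement (Power Analysis) that attrition will not exceed 10%.

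**3. How many might be erased (rates assumed; the documents give none)**

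| Assumed share of 88 | Youths erased | Share of the allowance of 8 |
|---|---|---|
| 0% (rule stops at randomisation) | 0 | 0% |
| 1% | 0.88 | 0.88/8 = 11% |
| 3% | 2.64 | 2.64/8 = 33% |
| 5% | 4.40 | 4.40/8 = 55% |

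**4. How far an estimate could move (illustration only)**

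Take a continuous outcome with 88/2 = 44 per arm. Suppose k youths are erased from one arm only, and their mean differs by 1 SD from those kept. That arm's mean moves by k/44 SD.

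For comparison, if the SAP's R² = 0.05 is read as the effect of a two-arm treatment indicator, f² = 0.05/0.95 = 0.0526 and d = 2 × √0.0526 = 0.459. The SAP does not state that reading; it is an assumption made here. The last column gives the approximate rise in the standard error, √(88/(88 − k)).

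| k | Shift k/44 (SD) | Shift/0.459 | Standard error multiplied by |
|---|---|---|---|
| 1 | 0.023 | 5% | 1.006 |
| 2 | 0.045 | 10% | 1.012 |
| 4 | 0.091 | 20% | 1.024 |

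These shifts need every erased youth to be in one arm and to be a full SD away from the rest. With no difference from those kept, the expected shift is 0 and only the last column applies.

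**The case against.** The strongest reply is that the rule concerns screening. It sits under Confidentiality and starts from assent and consent. Section 21 describes an assessment at Juvenile Services Department (JSD) intake and has project staff approach youths already regarded as eligible. Section 10 (Instrumentation) builds the listed measures into the baseline questionnaire, among them an adolescent severity inventory that covers mental health. Randomisation waits until baseline data are logged. There is thus a natural checkpoint after consent and before randomisation, which gives *later* an ordinary meaning, while section 10 governs those who have entered. This stands as a plausible account of the intent. It does not settle the matter, because no section says that the rule stops at randomisation and staff would have to apply it as written.

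Three stronger readings are tempting, and the documents do not support them:

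- **Youths who turn 18.** A reader might infer that a 17-year-old at entry is erased on reaching 18. Section 5 makes age a criterion for selection. A plan that recruits 17-year-olds, treats for 16 weeks and follows up to 12 months after the intervention must expect 18-year-olds in follow-up. Section 22 also gives the age range as 13 to 16, so a count of such youths would have no firm basis.
- **Youths who are incarcerated.** Not being incarcerated is an entry criterion, so a reader might infer that a re-arrested youth is erased, which would tie erasure to the recidivism outcome. Nothing makes incarceration a trigger. Section 10 withholds urine collection from youths held more than two days and searches jail and corrections records for youths who cannot be located. Both suggest that they stay in follow-up.
- **A second, unconditional rule in section 27.** Taken literally, that sentence would destroy the whole trial's data. It refers to a participant not mentioned before it there, and it looks carried over from section 26. It needs tidying but is weak evidence of a separate rule.

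It is also fair to say that the size is wholly assumed, that the SAP calls its analyses preliminary, and that the rule protects the privacy of minors in the justice system.

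**Conclusion.** The point holds in a limited form. Section 26 states a rule with no cut-off at randomisation. If it is applied to a youth found after randomisation never to have been eligible, it cannot be reconciled with following all entrants and analysing by intent to treat, and the loss cannot be undone.

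If the rule was meant to end at randomisation, no randomised youth is lost and only the wording is at fault. Otherwise the number is unknown and probably small: 0.9 to 4.4 of 88 on assumed rates of 1% to 5%. A reader might infer that the treatment comparison will be biased. The documents do not support that: they do not say whether detection would differ by arm, the direction is unknown, and the bias may be zero. The shifts of 0.02 to 0.09 SD are illustrations on assumptions chosen to be unfavourable. Severity: minor, and worth correcting because the correction is cheap and the loss would be permanent.

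**What to change.** Reconcile section 26 with the follow-up and intent-to-treat text in section 10, and bring the section 27 sentence into line:

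1. State that eligibility is fixed at baseline, and that destruction applies only to youths found ineligible before randomisation.
2. State that every randomised youth is kept, followed and analysed in the assigned arm unless consent for use of the data is withdrawn.
3. Log ineligibility discovered after randomisation by arm and reason, so that a sensitivity analysis can exclude those youths.
4. If the consent and assent forms repeat the assurance of destruction, amend them to match. The forms were not available for this review.

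This concerns data and analysis only, not whether therapy continues.

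The cost is a short wording change in sections 26 and 27, and possibly in the consent forms. The downside is that a few more sensitive records, including those of youths who should not have been enrolled, are retained under the planned Certificate of Confidentiality.
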